4.1 Concise description of the primary and secondary assessment criteria

4.1.1 Primary assessment criterion

Modified Rankin Scale (mRS) assessed at 6 months in a structured face-to-face interview. Favorable outcome is defined by an mRS score 0 to 2, and unfavorable outcome by a mRS from 3 to 6. (Appendix 1)

The Modified Rankin scale allows to score the functional state. It is the most widely used outcome in patients with SAH¹⁷. It can be passed in a face-to-face interview by physicians, physical therapists, a research assistant or research nurses. Its overall agreement is 81% ($\kappa=0.74$, $kw=0.91$) when structured interview is used and displays an excellent repeatability.

4.1.2 Secondary assessment criteria

The main pitfall of the modified Rankin Scale is the overrating of patients that develop cognitive impairment. We thus chose to assess separately cognitive impairment with using specific scales, including the MOCA, ADL and IADL. The SAHOT (SAH-outcome tool) will be finally assessed, as it has been recently developed and validated but not yet commonly used as the mRS¹⁸.

1. SAHOT score (Appendix 2)
2. MOCA score at 6 months (Appendix 3)
3. Return to work at 6 months
4. Activities of Daily Living (ADL) at 6 months (Appendix 4)
5. Instrumental Activities of Daily Living (IADL) at 6 months (Appendix 5)

Other generic morbidity criterion will be used.

6. Length of Intensive Care Unit (ICU) stay
7. Length of hospital stay
8. 28-day mortality

We will also assess the occurrence of cerebral vasospasm, delayed cerebral ischemia and new cerebral infarction as they represent potential confounding factors. Of note cerebral vasospasm diagnosis will be left to the discretion of physician as the strategy to undergo arterial MR/CT scan or DSA differs widely across centres but interpretation of these exams will be requested to be standardized in all participating centres. As aforementioned, New cerebral infarcts will be considered when detected on the CT scan or MRI performed with 6 weeks, (or on the latest CT scan or MRI performed before death within 6 weeks, or at autopsy), but not present on the earlier CT or MRI scan performed between 24 and 48 h after early aneurysm occlusion and not ascribable to other causes

9. Occurrence of DCI during the ICU stay

DCI will be defined as the occurrence of

- Focal neurological deficit (such as hemiparesis, aphasia, apraxia, hemianopia, or neglect), or
- Decrease of at least 2 points on the Glasgow Coma Scale (either on the total score or on one of its components [eye, motor on either side, verbal]).

➤ for at least 1 hour,
 ➤ not apparent immediately after aneurysm occlusion, and
 ➤ cannot be attributed to other causes by means of clinical assessment, CT or MRI scanning of the brain, and appropriate laboratory studies

10. Occurrence of cerebral vasospasm on a brain imaging on digitally substracted angiography (DSA) or Magnetic resonance/computed tomography angiogram (MR/CTA) performed upon clinical signs of delayed cerebral ischemia or severe impairment of cerebral blood velocity in transcranial doppler

Cerebral Vasospasm diagnosis will be defined upon DSA or MR/CTA.

On angiograms in DSA or MR/CTA, the severity of vasospasm will be considered none or mild if there is a less 33% decrease in arterial diameter on angiography, moderate if there is a 34% to 66% decrease, or severe if there is at least a 67% decrease.

DSA or MR/CTA will be performed when:

- There are signs of delayed cerebral ischemia as described above.
- There is a severe impairment of cerebral blood flow velocity assessed with help of transcranial doppler (tCD), as defined below. tCD will be performed at the discretion of the physicians in charge. tCD is a non-invasive radiation free exam that can be used at bedside. Its repetition allows a better detection of vasospasm and is routinely performed. Cerebral vasospasm severity will be evaluated according to this scale:

Degree of cerebral blood velocity alteration	Mean flow velocity (cm/s)	Lindegaard ratio
Mild	120-149	3-6
Moderate	150-199	3-6
Severe	>200	>6

11. Occurrence of new cerebral infarcts

New cerebral infarct is considered when detected on the CT scan or MRI performed with 6 weeks, (or on the latest CT scan or MRI performed before death within 6 weeks, or at autopsy), but not present on the earlier CT or MRI scan performed between 24 and 48 h after early aneurysm occlusion and not ascribable to other causes such as surgical clipping or endovascular treatment. Hypodensities on CT imaging resulting from ventricular catheter or intraparenchymal hematoma should not be considered cerebral infarctions secondary to DCI.

12. Occurrence of cilostazol-related major adverse events, including: arrhythmia, abnormal bleeding and allergy.
13. Occurrence of cilostazol-related minor adverse events include: tachycardia, fever, fainting, nausea, vomiting and stomach pain.

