2.3 Summary of relevant pre-clinical experiments and clinical trials

To date, four randomized controlled trials have assessed cilostazol in improving long-term outcome of adult patients with SAH.

In 2011, Suzuki and al. published the first prospective placebo-controlled study evaluating cilostazol in SAH patients¹². A hundred patients were enrolled: although cilostazol did not significantly decrease the incidence of symptomatic vasospasm (37.3% in the control vs. 22.4% in the cilostazol group, $p = 0.18$) and cerebral infarction (27.5% in control vs. 10.2% in the cilostazol, $p = 0.09$). However, the modified Rankin scale at discharge was significantly improved: 2.6 in controls vs. 1.5 in the cilostazol group, $p = 0.041$.

Senbokuya and al. published a second randomized controlled trial in 2013¹³. In this study, data from 109 patients were analysed. Symptomatic vasospasm, angiographic vasospasm and incidence of new cerebral infarctions were significantly lower in the cilostazol group, respectively 13 vs. 40% $p=0.0021$, 50 vs. 77% $p=0.006$, and 11 vs. 29% $p=0.03$. Nevertheless, no statistically significant difference was found regarding mRS at 1, 3 and 6 months but the cilostazol group tended to have better outcomes defined as an mRS 0-2; at 6 months, 88.9% patients and 74.5% had a good outcome in the cilostazol and placebo groups, respectively $p=0.08$. The number of adverse events in both groups was similar.

Matsuda et al. in 2016 included 148 patients in a randomized placebo-controlled study¹⁴. Occurrence of symptomatic vasospasm was significantly less frequent in the cilostazol group: 10.8 vs. 24.3%, $p = 0.031$, as well as the proportion of patients with poor outcome: 5.4 vs. 17.6%, $p = 0.011$. Multiple logistic analyses showed that cilostazol administration was an independently associated with reduced poor outcome: OR 0.221, 95% CI 0.054–0.903, $p = 0.035$.

Sugimoto et al. in 2018 included 50 cases that were randomly assigned to cilostazol (n=23) and placebo (n=27) groups¹⁵. Among the 48 analysed patients, those from the cilostazol group tended to have a better clinical outcome than those from the control group, according to the eGOS at 6 months after SAH (74% versus 56%). This difference was however not statistically significant (odds ratio 1.437, 95% CI 0.376 to 5.483, $P=0.596$).

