12 STATISTICAL ASPECTS

12.1 Description of statistical methods to be used including the timetable for the planned interim analyses

CASH is a multicentre, double-blinded, randomised, placebo-controlled, parallel-group superiority trial in adult, using an adaptive group-sequential design, to demonstrate that cilostazol plus nimodipine is safe and superior to nimodipine alone will improve modified Ranking Score (mRS) at six months.

Two interim analyses for futility and efficacy are planned.

Populations

For the statistical analysis, the following populations are defined:

Population	Description
Intent-To-Treat (ITT) Population	The ITT population will include all randomised participants. ITT participants will be analysed according to the randomised treatment, regardless of the actual treatment received. All efficacy analyses will be performed on the ITT population.
Per Protocol (PP) Population	The PP population will include all participants in the ITT with at least 80% of doses received to define adherence to treatment. The PP population will be used for supportive analyses of efficacy measures.
Safety Population (SP)	The SP will include all randomised participants who received at least one treatment (active or placebo). The SP will be analysed according to the actual treatment received. This population will be used for safety analyses.

Description of the statistical methods, including the timing of planned interim analyses

The statistical analysis plan (SAP) will be developed and finalised before the database is locked.

Below is a description of the planned statistical analysis. Further details will be presented in the statistical analysis plan (SAP).

All statistical analyses will be performed with SPSS version 26 or RStudio. For analyses performed with RStudio, the script used will be provided.

The baseline is defined as the last evaluation performed before the start of the study treatment, day 1 (V1).

All data collected after the start of the study treatment are defined as post-baseline.

Baseline characteristics will be summarised by the treatment group. The mean and standard deviation (SD) or median and interquartile range (IQR) for skewed variables will be summarised for continuous measures.

The proportion in each category will describe categorical variables.

In addition, the 95% confidence interval (CI) will also be calculated as indicated.

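### Endpoint 10 records vasospasm on angiography triggered by DCI signs or a severe Doppler, while the objective is vessel narrowing itself, so an effect on DCI can look like an effect on vessels

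*Protocol*

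**What the plan says.** Three parts of the Protocol bear on this point.

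**The endpoint.** Section 4.1.2, item 10 counts vasospasm on DSA or MR/CT angiography "performed upon clinical signs of delayed cerebral ischemia or severe impairment of cerebral blood velocity in transcranial doppler", and adds: "Cerebral Vasospasm diagnosis will be defined upon DSA or MR/CTA". It then lists the two occasions for angiography: "There are signs of delayed cerebral ischemia as described above" and "There is a severe impairment of cerebral blood flow velocity assessed with help of transcranial doppler (tCD), as defined below". The Doppler trigger is the severe grade only (mean velocity above 200 cm/s, Lindegaard ratio above 6). The Doppler itself is optional: "tCD will be performed at the discretion of the physicians in charge". The introduction to the imaging endpoints says that "cerebral vasospasm diagnosis will be left to the discretion of physician", because angiography practice varies between centres; only the reading is to be standardised. Section 5.2 collects Doppler and angiography results when they exist. The scheduled scans in the synopsis and Section 5.2 are brain imaging and are not described as angiography.

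**The objective.** Section 3.2 lists vasospasm among the outcomes on which the effect of cilostazol is assessed. It defines it as reduced diameter of the proximal vessels on any CT, MR or catheter angiogram. The synopsis and Section 5.3 do the same. None of the three mentions a trigger.

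**The analysis.** Section 12.1 states: "All efficacy analyses will be performed on the ITT population", and repeats this for secondary efficacy analyses. It gives no specific rule for a patient who never had an angiogram.

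**The concern.** The objective asks how many patients had narrowed vessels. Item 10 records how many had narrowed vessels and were also imaged for one of two reasons. The first reason, DCI, is an outcome that the drug is expected to change: Section 2.1 hypothesises benefit through a lower DCI rate. If that is right, the chance of being imaged differs by arm after randomisation. Blinding does not prevent this, because the difference comes from the drug's own effect. Adjudication and standardised reading cannot recover angiograms that were never taken.

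At stake is a mechanistic conclusion. Section 2.1 argues that DCI involves more than vasospasm and that reducing angiographic vasospasm has not been shown to reduce DCI. The trial therefore has reason to separate the two, and item 10 as defined cannot do so. A fall in DCI with no change in vessel calibre could be reported as fewer vasospasms.

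**Working it through.** **What the plan computes.** The Protocol gives no rate, power or sample size for item 10, so there is no figure of its own to reproduce. Only the denominator is taken from the design in Section 12.5: 315 per arm. That design reproduces (simulated power 0.800 with the stated boundaries, against 0.8016 stated) and is not in question.

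**Model.** In each arm let V be the true share with angiographic vasospasm, D the share with DCI, and q the share of vasospasm without DCI that is imaged by the Doppler route or otherwise. Assume that every DCI patient is imaged and positive, and that unimaged patients count as negative. Then:

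- detected rate = D + q × (V − D)
- share of true vasospasm missed = (1 − q) × (V − D) / V

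**Case 1: no effect on vessels.** V = 60% in both arms (assumed). D = 30% in control, from the approximate rate in Section 2.2, and 21% on cilostazol (assumed, a 30% relative reduction).

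| q | Control detected | Cilostazol detected | Risk ratio | Missed, control / cilostazol |
|---|---|---|---|---|
| 0 | 30.0% | 21.0% | 0.70 | 50% / 65% |
| 0.25 | 37.5% | 30.75% | 0.82 | 37.5% / 48.8% |
| 0.50 | 45.0% | 40.5% | 0.90 | 25% / 32.5% |
| 0.75 | 52.5% | 50.25% | 0.96 | 12.5% / 16.3% |
| 1 | 60.0% | 60.0% | 1.00 | 0% / 0% |

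For example, at q = 0.25 the control rate is 0.30 + 0.25 × 0.30 = 0.375 and the cilostazol rate is 0.21 + 0.25 × 0.39 = 0.3075.

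Chance of nominal two-sided p < 0.05 with 315 per arm (normal approximation): at q = 0 the standard error is √[(0.30 × 0.70 + 0.21 × 0.79)/315] = 0.0345, so z = 0.09/0.0345 = 2.61 and the chance is about 74%. For q = 0.25, 0.50 and 0.75 it is about 43%, 21% and 8 to 9%, against 5% with no bias.

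**Case 2: DCI independent of vasospasm.** This drops the assumption that every DCI patient has vasospasm. Detected rate = V × [1 − (1 − D)(1 − t)], where t is the chance that a patient with vasospasm has a severe Doppler recorded. With V = 77% in both arms and D = 30% versus 21%:

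- t = 0: 23.1% versus 16.2%, risk ratio 0.70
- t = 0.3: 39.3% versus 34.4%, risk ratio 0.88
- t = 0.5: 50.1% versus 46.6%, risk ratio 0.93
- t = 1: 77% in both arms, risk ratio 1.00

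**Case 3: figures cited in Section 2.3.** For the 2013 trial the Protocol reports that "Symptomatic vasospasm, angiographic vasospasm and incidence of new cerebral infarctions were significantly lower in the cilostazol group": 13% versus 40% symptomatic and 50% versus 77% angiographic. Let symptomatic vasospasm stand in for DCI (an assumption). If only symptomatic patients had been imaged, the recorded rates would be 13% versus 40%, a risk ratio of 0.33, instead of 50/77 = 0.65. The missed share would be 37/77 = 48% in control and 37/50 = 74% on cilostazol. At q = 0.25, 0.50 and 0.75 the risk ratio would be 0.45, 0.54 and 0.60. A real vessel effect would be exaggerated in the same direction.

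**Other ways of handling unimaged patients.** Excluding them conditions on a post-randomisation event that treatment is expected to change. Treating them as missing and imputing would borrow from patients selected for symptoms or severe velocities. Neither recovers the angiograms not taken.

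**The case against.** A reader might infer that the plan counts every unimaged patient as free of vasospasm. No sentence says so for item 10. Section 12.1 names an analysis population, not a coding rule. Its missing-data paragraph provides a multiple-imputation sensitivity analysis for other variables when more than 10% of subjects are missing, and it defers detail to the SAP. Counting unimaged patients as negative is the natural reading of the all-randomised rule, but it remains an inference.

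A reader might also infer that vasospasm can be seen only in triggered patients. That is too strong. Sections 3.2 and 5.3 accept any angiogram, Section 5.2 collects whatever was done, and diagnosis is left to the physician. Section 4.1.2 also calls repeated Doppler routine. This makes q = 0, the source of the most striking figures, the least credible case. At q = 0.75 the risk ratio is 0.96.

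The inputs are also soft. The values of q and t, the 21% and the 60% are assumptions. The 2013 trial's symptomatic vasospasm is not DCI as defined here, and Section 2.3 does not say how that trial scheduled its angiograms. Case 1 makes every DCI patient positive, which sits badly with the view that DCI is more than vasospasm; Case 2 drops that assumption and gives ratios nearer 1 at t = 0.3 and 0.5.

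All of this limits the size and certainty of the bias. It does not remove the mechanism, since only severe Doppler grades prompt imaging and the Protocol concedes that practice differs between centres. Nor is it only SAP detail: the trigger stands in the Protocol's endpoint definition and does not match its objective.

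**Conclusion.** The concern holds as a mismatch between objective and endpoint, with detection that depends on an event the drug is expected to reduce. If cilostazol lowers DCI, vasospasm will probably be under-detected, and more so in the cilostazol arm, however unimaged patients are coded. The models quantify only the count-as-negative reading.

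Under the Case 1 assumptions the spurious risk ratio runs from 0.70 (q = 0) to 0.96 (q = 0.75) and vanishes only at q = 1. The true size cannot be derived from the document. The firmer statement that a drug acting only on DCI will show a vasospasm benefit is not supported: it can, and how often depends on how much vasospasm without DCI is imaged.

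This is one of thirteen secondary criteria. The primary mRS analysis and the sample size are unaffected. It should be corrected because the claim about vessels would otherwise be uninterpretable.

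**What to change.** No added imaging and no change in care are needed.

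1. Align the synopsis and Sections 3.2 and 5.3 with item 10. Name the endpoint *clinically or Doppler-triggered angiographic vasospasm*. State that the main analysis compares detected events in all randomised patients and is not an estimate of the effect on vessel calibre.
2. Record in the e-CRF whether angiography was done and why (DCI sign, Doppler, other). Report the number imaged and the trigger by arm.
3. Keep *not imaged* distinct from *imaged, no vasospasm* in the data.
4. Add a sensitivity analysis that varies the vasospasm rate in unimaged patients, separately in each arm, from 0% up to the rate in Doppler-triggered patients without DCI. That upper limit is probably high, because those patients were selected for severe velocities. Setting 0% in both arms returns the main analysis. Claim an effect on vessel calibre only if the difference survives the whole range.

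The cost is Protocol and SAP wording, one extra e-CRF field that must be collected prospectively because reasons for imaging are hard to reconstruct later, and a more hedged claim on one secondary endpoint.

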5.2 Follow-up Visits

Follow up visits will be performed daily from day 1 to day 28. One Brain imaging will be realized 24/48 hours after the aneurism treatment and one between day 28 and 45 after randomization. Transcranial doppler, MR CTA or DSA results will be collected when realized.

Day 1 to day 28

Vital status

Compliance to treatment

Experimental Treatment administration will be collected daily

Safety follow up

- Any major Cilostazol-related adverse event will be assessed:
 - Arrhythmia from auricular origin
 - Arrhythmia from ventricular origin
 - Abnormal bleeding
 - Allergy
- Other minor Cilostazol-related adverse events:
 - Tachycardia,
 - Fever
 - Fainting
 - Nausea
 - Vomiting
 - Stomach pain

Cerebral vasospasm

- Blood flow velocity increase on TCD
- Cerebral vasospasm diagnosed upon MR/CTA or DSA and its severity (mild/moderate/severe)

Delayed cerebral ischemia

- New focal deficit
- Glasgow point decrease
- No other cause

Treatment in the last 24 hours

- Continuous sedation
- Mechanical ventilation
- Extraventricular drain
- Therapy Intensity Level (TIP) for Raised ICP treatment (See Appendix 7)
- Hypertension therapy
- Vasopressors (epinephrine/norepinephrine/dobutamine)
- Milrinone administration
- Endovascular treatment (Balloon therapy or vasodilatator administration)
- Other treatment
- At ICU discharge, the modified Rankin scale will be evaluated by a blinded research technician in case of lost to follow up.

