10.3.1 Definitions (Regulation (EU) N° 536/2014 (REC)

Adverse event Any untoward medical occurrence in a patient or clinical trial subject administered a medicinal product and which does not necessarily have a causal relationship with this treatment.

- **Adverse drug reaction**

Any response to a medicinal product which is noxious and unintended.

- **Serious adverse event**

Any untoward medical occurrence that at any dose results in death, is life-threatening, requires inpatient hospitalisation or prolongation of existing hospitalisation, results in persistent or significant disability/incapacity, or is a congenital anomaly/birth defect.

- **Unexpected adverse reaction**

An adverse reaction, the nature, severity or outcome of which is not consistent with the applicable product information: the summary of product characteristics (SmPC) for an authorised product or the investigator's brochure for an unauthorised investigational product.

According to the notice to sponsors of clinical trials for medications (ANSM):

- **New safety issue**

Any new information regarding safety:

- that could significantly alter the assessment of the benefit-risk ratio for the experimental medication, or for the trial
- or which could lead to the possibility of altering the administration of the experimental medication or altering the conduct of the trial

Examples:

- a) any clinically significant increase in the frequency of an expected serious adverse reaction occurring
- b) suspected unexpected serious adverse reactions (SUSAR) occurring in patients who have finished the trial and about whom the sponsor is notified by the investigator, who also provides any follow-up reports
- c) any new fact relating to the conduct of the clinical trial or the development of the experimental medication, if the new fact is likely to affect participant safety

Examples:

- a serious adverse event likely to be related to the investigations and to the trial's diagnostic procedures and which could modify the conduct of this trial
- a significant risk for the trial participants such as ineffectiveness of the experimental medication used in the trial in treating a life-threatening illness
- significant safety results from a recently completed research carried out on animals (such as a carcinogenicity research)
- the premature termination, or temporary interruption, of a trial conducted with the same experimental medication in another country, for safety reasons

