10.3.2.2 The investigator's other roles

The investigator must document the serious adverse event as thoroughly as possible and provide the medical diagnosis, if possible.

The investigator assesses the severity of the adverse events by using an adverse events rating scale, attached to the protocol, by using general terms:

- *Mild: tolerated by the patient, does not interfere with daily activities*
- *Moderate: sufficiently uncomfortable to affect daily activities*
- *Serious: preventing daily activities*

The investigator assesses the causal relationship between the serious adverse events and the experimental medication(s) added by the research.

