10.3.3 Specific features of the protocol

All serious and non-serious adverse events must be reported in the CRF.

10.3.3.1 Serious adverse events that do not require the investigator to immediately notify the sponsor

These serious adverse events are only recorded in the "adverse event" section of the case report form.

- **Normal and natural evolution of the pathology:**

Normal and natural evolution of aneurismal SAH is quite variable:

- Even without initial neurological deficit, patients are closely monitored after securisation of the aneurism because of the risk of DCI, vasospasm, hydrocephalus, rebleeding, or any other unspecific complication. Patients in worse neurological condition can be initially intubated; the duration of mechanical ventilation dependst on the subsequent neurological improvement and intercurrent ICU complications.
- Securisation of the aneurism can be performed with endovascular coiling or surgical clipping and lead to ischemic stroke

- Death occurs in approximately 30% of all cases.
- DCI can occur from day 4 until the 21th day after SAH. This risk peaks about the 10th day. DCI can require hypertension therapy and infusion of vasopressor, adjunctive pharmacological treatment, notably milrinone, and endovascular treatment of vasospasm can be requested, but in a centre-dependant way
- Other organ failure might occur as patients might require prolonged ventilatory support and developed ICU related complications, such as nosocomial infection.
- Initial hydrocephalus can worsen the neurological status; it can occur from the first to 15th day. It can require an external ventricular drain. The drain can often be weaned during hospitalisation but if not, internal ventricular drainage can be implanted. It is associated with a risk of nosocomial menigitis.
- When the risk of DCI or other neurological complication is considered low enough, the patient is transferred to the ward until the patient is discharged from the hospital to either the patient's home or a rehabilitation centre.
- **Adverse events likely to be associated with the treatments prescribed as part of the patient's care during the monitoring of the research**

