12.4 Statistical Analysis and Sensitivity Tests

To ensure robust conclusions, we will apply multiple sensitivity analyses, in addition to ITT and PP analyses:

1. Complete Case Analysis (excluding patients with missing data).
2. Multiple Imputation of missing data to assess the impact of lost-to-follow-up cases.
3. Scenario analysis excluding non-neurological deaths.

Safety analysis

For each patient and each type of toxicity described according to the CTCAE (V.5.0), the worst-case category identified during treatment will be used for the descriptive analysis.

Safety Measures

Safety will be assessed using:

- Incidence of treatment-related adverse events (TEAEs)
- Incidence and severity of treatment-emergent adverse events (TEAEs)
- Incidence of serious adverse events (SAEs)
- Incidence of TEAEs and SAEs leading to discontinuation of study medication.
- Changes in blood chemistry, hematology and coagulation parameter results
- Changes in vital signs including temperature, pulse, respiratory rate, systolic and diastolic blood pressure
- Changes in physical examination results
- Changes in electrocardiogram (ECG) results

These data will be described using lists and tables.

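### Safety endpoints 12 and 13 are worded as cilostazol-related events with no rule for deciding relatedness; they should count every listed event by arm

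*Protocol*

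**What the plan says.** The two safety items among the numbered secondary criteria in Protocol section 4.1.2 both carry a relatedness qualifier. Item 12 reads "Occurrence of cilostazol-related major adverse events, including: arrhythmia, abnormal bleeding and allergy". Item 13 reads "Occurrence of cilostazol-related minor adverse events include: tachycardia, fever, fainting, nausea, vomiting and stomach pain".

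The qualifier recurs. The monitoring sentence at the end of section 3.2 (run together with the heading of section 4) uses it. So does the daily follow-up list in section 5.2: "Any major Cilostazol-related adverse event will be assessed" and "Other minor Cilostazol-related adverse events".

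On who judges cause, section 10.3.2.2 says: "The investigator assesses the causal relationship between the serious adverse events and the experimental medication(s) added by the research". Section 4.2.5 blinds participants, care providers and outcome assessors.

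Elsewhere the protocol is neutral about cause. Section 10.3.1 defines an adverse event as one "which does not necessarily have a causal relationship with this treatment". Section 10.3.3 states: "All serious and non-serious adverse events must be reported in the CRF". The safety measures in section 12.4 open with "Incidence of treatment-related adverse events (TEAEs") and then list, as separate lines, the incidence and severity of treatment-emergent events and the incidence of serious events, neither limited by cause.

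**The concern.** Read literally, an event enters endpoint 12 or 13 only if someone decides that cilostazol caused it. In a double-blind trial that person does not know whether the patient received cilostazol. These patients also bleed, become febrile and develop complications for other reasons: section 10.3.3.1 lists rebleeding, nosocomial infection and drain-associated meningitis as part of the natural course. A bleed or a fever could therefore be put down to the haemorrhage or to intensive care and leave the endpoint.

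Randomisation with placebo already allows a comparison of all listed events between arms without any attribution. A relatedness filter adds a judgement whose quality the protocol does not control, in the numbered endpoints that bear most directly on the aim in section 4.2.1 of showing that the combination is safe.

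**Working it through.** The protocol states no event rate, attribution rate, margin or power for items 12 and 13, so there is no figure to reproduce. The check is mainly a comparison of sections.

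**1. Is there a rule for relatedness?**
- Sections 3.2, 4.1.2 and 5.2 use the qualifier and give no criterion.
- Section 10.3.2.2 gives the investigator a causality judgement for serious events. Item 13 consists of minor events, and item 12 can include non-serious ones: section 10.3.3.3 itself lists well-tolerated arrhythmias as not serious.
- Section 10.3.6.1 has the sponsor assess the causal relationship of reported events, but does not link this to items 12 and 13.
- Section 9.3 gives a blinded committee the adjudication of secondary endpoints, with its opinion taking precedence. If that covers items 12 and 13, it settles who has the last word but not the criterion.

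**2. Can the wording be read in two ways?**
- *Attribution reading:* count a listed event only when it is judged to be caused by cilostazol.
- *Event-type reading:* count any event of a type known for cilostazol. Item 12's three types are the major side effects named in section 2.7, and section 10.3.3.3 lists item 13's six events with no relatedness condition.

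The two readings give different counts from the same case report forms, and no section chooses between them.

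**3. Is an all-cause description available?** Yes. Section 10.3.3 has all events recorded. Section 12.4 describes all treatment-emergent events, all serious events and the worst CTCAE category per patient and toxicity type. Section 12.1 supplies a safety population grouped by treatment actually received. Section 12.4 says that the safety data are to be described in lists and tables, so it plans no test.

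**4. What could a filter do? A purely hypothetical illustration.** Only n = 315 per arm (section 12.5) comes from the protocol. All rates below are assumed, and so is the two-sided 5% comparison.

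Let p0 and p1 be the true event rates on placebo and cilostazol, b the share of background events labelled related, and d the share of drug-caused events labelled related. The filtered rates are b·p0 on placebo and b·p0 + d·(p1 − p0) on cilostazol.

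Power = Φ[(difference − 1.96·SE0)/SE1], where SE0 = √(2·p̄(1 − p̄)/n), p̄ is the mean of the two rates, and SE1 = √([p0(1 − p0) + p1(1 − p1)]/n), using the filtered rates where a filter applies.

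With p0 = 5% and p1 = 10%:

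| Counting rule | Placebo | Cilostazol | Calculation | Power |
|---|---|---|---|---|
| All events | 5% | 10% | (0.05 − 0.0411)/0.0209 = 0.42 | 66% |
| Label unrelated to true cause, b = d = 0.5 | 2.5% | 5% | (0.025 − 0.0297)/0.0151 = −0.31 | 38% |
| Informative label, b = 0.2, d = 0.8 | 1% | 5% | (0.04 − 0.0266)/0.0135 = 0.99 | 84% |

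The direction depends on how good the attribution is. In the third row the absolute excess falls from 5 to 4 points, but the rate ratio rises from 2 to 5 and so does the power. The protocol fixes neither b nor d.

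**The case against.** The strongest reply is that no filter was intended. Section 5.2 is a daily checklist of event types with no causality item. Where the authors want other causes excluded, as for delayed cerebral ischaemia and new infarcts, they say so. And if investigators judge cause only for serious events, there is no investigator judgement by which a minor event could leave endpoint 13. This reading is plausible and may be the intended one. It is not stated, however, and under it the proposed wording merely records the intent.

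The second reply is that a real excess would be seen anyway. This stands. A reader might infer from items 12 and 13 that the protocol makes no all-cause safety assessment; sections 10.3.3 and 12.4 show otherwise.

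A reader might also infer that a relatedness filter must weaken the comparison. The third row of the table shows that this does not follow.

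Finally, section 12.4 attaches one abbreviation, TEAEs, to both treatment-related and treatment-emergent events. A reader might conclude that the two cannot be told apart. Both are spelled out in full, so this is a clerical slip.

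**Conclusion.** The concern holds as a moderate defect of definition confined to endpoints 12 and 13 and the matching text in sections 3.2 and 5.2. The qualifier has no decision rule. Its literal meaning needs blinded attribution that the protocol describes for investigators only for serious events, and its alternative meaning gives a different count.

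The documents do not support saying that the protocol lacks an all-cause safety description or that harm would be hidden: section 12.4 would still show an excess, though descriptively. No size can be given, because event rates and attribution quality are not stated; the power figures are hypothetical and show only that the effect could go either way. An all-occurrence count does not depend on attribution quality.

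**What to change.** - **Section 4.1.2, items 12 and 13:** define each as any occurrence of the listed event types in either arm, from day 1 to day 28 (the follow-up window of section 5.2), whatever the judged cause, compared by arm in the safety population. Report relatedness only as a supportive descriptive column.
- **Sections 3.2 and 5.2:** remove the relatedness qualifier so that the objective and the daily collection list match.
- **Section 12.4:** as a tidy-up, keep TEAE for treatment-emergent events and name treatment-related events separately.

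The cost is wording in four sections. Section 10.3.3 already requires every adverse event to be recorded, so no new data are needed, and no clinical rule changes.
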